**Table 2 Analysis Visit Windows**

Study Period	Nominal Visit	Nominal Day	Visit Window (day)
Screening	Screening	-30 to -1	-30 to -1
Placebo-Controlled, Double-Blind	Day 1	1	1 (Pre-dose)
	Week 4	29	1 (Post-dose) to 42 (Pre-dose)
	Week 8	57	43 to 70 (Pre-dose)
	Week 12	85	71 to 108 (Pre-dose)
	Week 16	113	109 to 136 (Pre-dose)
Treatment Extension	Week 16	113	109 to 136 (Pre-dose)
	Week 20	141	137 to 164 (Pre-dose)
	Week 24	169	165 to 192 (Pre-dose)
	Week 28	197	193 to 220 (Pre-dose)
	Week 32	225	221 to 248
	Week 36	253	249 to 275

	Week 40	281	276 to 286
--	---------	-----	------------

Study Day and Day of Assessment or Event definitions are provided in **Appendix 1**.

### 6.2.2 Primary Efficacy Variable

The primary endpoint for this study is the **change from baseline in abscess and inflammatory nodule (AN) count at Week 16**. The AN count is defined as the sum of the number of abscesses and inflammatory nodules (from all locations) from the CRF. For the change from baseline in AN count, the difference in AN count taken between Week 16 and baseline will be computed for each treatment group and overall. The AN count will be assessed at the visits specified in the Schedule of Activities in **Section 3.6**.

### 6.2.3 Secondary Efficacy Variables

The secondary efficacy endpoints are as follows:

- **Percent change from baseline in AN count at Week 16**
- **Proportion of subjects achieving Hidradenitis Suppurativa Clinical Response 50 (HiSCR50) at Week 16**

The proportion of subjects with at least a 50% decrease from baseline AN count, and no increase in abscesses or draining fistulas in comparison to baseline (HiSCR50) at Week 16 will be calculated for each treatment group as follows:

A responder HiSCR50 is defined as a subject with

- a) at least a 50% decrease in AN count from Baseline, and
- b) no increase in abscess count relative to Baseline, and
- c) no increase in draining fistula count relative to Baseline

Having HiSCR50 data at Week 16 is defined as a subject who is either a responder HiSCR50 or can be confirmed to be a non-responder based on assessed data. Then, the proportion of subjects achieving HiSCR50 is defined as the following ratio:

$$\frac{\text{\# of subjects in treatment group achieving HiSCR50 responder status}}{\text{\# of subjects in treatment group having HiSCR50 data at Week 16}}$$

- **Change from baseline in worst HS Pain NRS scores at Week 16**
- **Percent change from baseline in worst HS Pain NRS scores at Week 16**
- **Change from baseline in average HS Pain NRS scores at Week 16**

- Percent change from baseline in average HS Pain NRS scores at Week 16

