#### 9.4.6 ANALYSIS OF THE SECONDARY EFFICACY ENDPOINTS

The ITT analysis set will be used for analysis of secondary efficacy endpoints. Following are the secondary efficacy endpoints:

- Percent change from Baseline in AN count at Week 16
- Proportion of subjects achieving HiSCR50 at Week 16

- Change from Baseline in HS Pain NRS at Week 16
- Percent change from Baseline in HS Pain NRS at Week 16

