#### 9.4.6.1 CATEGORICAL ENDPOINTS

Frequency and percentages for each response Yes/No for categorical endpoints will be presented separately by visit for each treatment arm. Subjects with missing scores at a given visit will be considered to have not met the criteria of interest (ie, nonresponse). Estimates of the difference between treatments (imsidolimab – placebo) will be presented along with exact 90% CIs. Treatment arms will be compared using Cochran–Mantel–Haenszel chi-squared test, adjusted for stratification factor (Hurley Stage at baseline (Stage II or III)).

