- Change from Baseline in PGIS at each visit
- Proportion of subjects in each category of Hurley Stage at each visit
- Change from Baseline in Hurley Stage at Weeks 16, 32, and 40
- Proportion of subjects achieving at least a 1-stage improvement in Hurley stage
- Skin tape strip and drainage fluid biomarkers analysis including, but not limited to, IL-36 and Th-17
- Presence of ADAs to imsidolimab
- Serum concentration following imsidolimab administration and other parameters as appropriate will be determined to describe the PK profile of imsidolimab

Methods for analyzing the above categorical and continuous efficacy endpoints will mirror the methods described in [Section 9.4.6.1](#) and [9.4.6.2](#), respectively. ITT analysis set will be used for analysis of exploratory efficacy endpoints.

As further additional exploratory analyses, the primary efficacy endpoint, all secondary efficacy endpoints, and some of the exploratory endpoints will be summarized using the Extension analysis population.

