## 1. INTRODUCTION

This Statistical Analysis Plan (SAP) outlines the statistical methods for the display, summary and analysis of data collected within the scope of the latest version of the ANB019-208 Protocol (Amendment 1, dated 24 September 2021). As with any SAP, the proposed methods and approaches to the data analysis should be deemed as flexible. The analysis of the data should allow changes in the plan to the extent that deviations from the original plan would provide a more reliable and valid analysis of the data. As such, the statistical analysis to a certain degree is iterative since much of the planning is based on assumptions that require verification. The purpose of this plan is to provide general guidelines from which the analysis will proceed. Nevertheless, deviations from these guidelines must be substantiated by a sound statistical rationale.

The SAP should be read in conjunction with the study protocol and the Case Report Forms (CRFs). This version of the SAP has been developed using the final version of the protocol mentioned above and the version of the annotated CRFs dated 22 December 2021.

This study is designed to evaluate the efficacy and safety of ANB019 in the treatment of subjects with Hidradenitis Suppurativa (HS). (See Protocol [Sections 2.1](#) to [2.3](#) for details).

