# 7. STATISTICAL ANALYSIS

## 7.1 Data Handling Rules and Definitions, Including Handling of Missing Data

Except where specified, all continuous variables will be summarized with descriptive statistics (the number of non-missing values, mean, standard deviation, first and third quartiles, median, minimum, and maximum). Where data have been logarithmically transformed for analysis, the summary statistics on the back-transformed data will include the geometric mean (calculated as  $\exp(m)$ ), where  $m$  is the mean of the data on the log scale) and the coefficient of variation (calculated as  $100\sqrt{[\exp(s^2)-1]}$ , where  $s$  is the standard deviation of the data on the log scale). All categorical variables will be summarized with frequency counts and percentages. Tabulations will be provided based on all subjects combined, as well as separately by treatment group.

Missing data will be maintained as missing in the analysis datasets, unless specified otherwise. For variables where missing data are imputed, the analysis dataset will contain a new variable with the imputed value and the original variable value will be maintained as missing.

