## 7.5.2 Secondary Efficacy Analyses

### 7.5.2.1 Percent change from baseline in AN count at Week 16

This secondary endpoint will be analyzed using a similar MMRM model as for the primary endpoint. The percent change from baseline in AN count at Week 16 will be the response variable.

### 7.5.2.2 Proportion of subjects achieving HiSCR50 at Week 16

The frequency and percentage of subjects with HiSCR50 will be summarized at Week 16. The unadjusted risk difference and 90% exact unconditional confidence intervals will be reported between the imidolimab and placebo groups for all subjects and Hurley Stage at randomization (Stage II or III). The common risk difference will also be tested using a generalized Cochran-Mantel-Haenszel test (ANOVA for row means), adjusting for Hurley Stage at randomization.

A sensitivity analysis will be conducted for this endpoint on the ITT Analysis Set where subjects received rescue medications between Week 4 and Week 16 will be considered as failure to achieve HiSCR50 at Week 16.

An additional exploratory analysis will be performed for the proportion of subjects achieving HiSCR50 by visit. A repeated-measures generalized estimating equations (GEE) with the logit link will be used. The model will include treatment, visit, treatment by visit interaction, race, gender, Fitzpatrick skin type, Hurley Stage at baseline, and baseline inflammatory lesion count as covariates. Data from protocol specified visits up to Week 16 will be included in the analysis. An unstructured correlation matrix will be used to model correlation within a patient; if convergence is an issue, a Toeplitz structure may be considered. An odds ratio resulting from this model along with 90% CI will be reported.

### 7.5.2.3 Change from Baseline in Average HS pain NRS at Week 16

Change from baseline in Average HS pain NRS at Week 16 will be analyzed using a similar MMRM model as for the primary endpoint, but changing baseline AN count to HS pain NRS in the model as the response.

### 7.5.2.4 Percent change from Baseline in Average HS pain NRS at Week 16

Percent change from baseline in Average HS pain NRS at Week 16 will be analyzed similarly to percent change from baseline in AN count at Week 16, as described in **Section 7.5.2.1**.

### 7.5.2.5 Change from Baseline in Worst HS pain NRS at Week 16

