## 8. CHANGES FROM METHODS PLANNED IN THE PROTOCOL

- The protocol uses the following spelling for the patient global impression questionnaires: “PGIS”, “PGIC”, and “PGIB”. This SAP uses the following spelling for the patient global impression questionnaires: “PGI-S”, “PGI-C”, and “PGI-B”.

- The protocol uses the term ‘major protocol violations’ in the definition of the Per Protocol Analysis Set. This SAP uses the term ‘important protocol deviations’ throughout.
- The protocol states that the primary estimand is comprised of four components. This SAP includes a fifth component, treatment condition, per ICH E9 (R1) addendum.
- The protocol has two secondary endpoints for PGI-C data with titles that begin “Proportion of subjects achieving improvement...”. This SAP uses the following titles to better distinguish between the two: “Proportion of subjects achieving much improvement...”, and “Proportion of subjects achieving improvement...”.

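### SAP Section 6.2.3 leaves subjects with undetermined Week 16 HiSCR50 status out of the denominator, the protocol counts them as nonresponders, and SAP Section 8 does not declare the change

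*SAP*

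**What the plan says.** Protocol 9.4.6 sets the population: "The ITT analysis set will be used for analysis of secondary efficacy endpoints". Protocol Table 7 defines that set as everyone randomised. Protocol 9.4.6.1 then gives the rule for categorical endpoints: "Subjects with missing scores at a given visit will be considered to have not met the criteria of interest (ie, nonresponse").

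SAP 6.2.3 defines the HiSCR50 proportion as a ratio. The numerator is responders. The denominator is subjects with HiSCR50 data at Week 16, explained as follows: "Having HiSCR50 data at Week 16 is defined as a subject who is either a responder HiSCR50 or can be confirmed" as a non-responder from what was assessed.

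SAP 7.5.2.2 describes the risk difference, exact confidence interval, Cochran-Mantel-Haenszel (CMH) test and an exploratory GEE. It gives no denominator or missing-data rule for any of them. Its one sensitivity analysis concerns rescue: "subjects received rescue medications between Week 4 and Week 16 will be considered as failure to achieve HiSCR50 at Week 16". SAP 7.1 adds a general rule: "Missing data will be maintained as missing in the analysis datasets, unless specified otherwise".

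SAP Section 8 lists four departures from the protocol: the spelling of questionnaire abbreviations, the term for protocol deviations, a fifth estimand component ("The protocol states that the primary estimand is comprised of four components"), and the titles of two PGI-C endpoints. None concerns HiSCR50 or missing categorical data.

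For the exploratory endpoints, Protocol 9.4.7 carries the same rule over: "Methods for analyzing the above categorical and continuous efficacy endpoints will mirror the methods described in" 9.4.6.1 and 9.4.6.2. SAP 6.2.4 nevertheless uses data-available denominators for HiSCR50 at other visits, HiSCR75, AN50, AN75, both HS-PGA responder endpoints, the PGI-C, PGI-B and PGI-S responder endpoints, and one-stage Hurley improvement. The two 3-point pain responder endpoints instead divide by all subjects with a baseline score of at least 3.

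**The concern.** The two documents give different answers for the same subject. Someone who leaves before Week 16, with nothing on record that settles HiSCR50 status, is a nonresponder under the protocol and is not counted under the SAP ratio. The SAP prints its denominator openly, but a reader is not told that it differs from the protocol.

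Under SAP 3.4 the secondary endpoints go into the Week 16 analysis that informs the sponsor's development decisions. HiSCR50 is the responder endpoint among them, so its reported rate and treatment difference should follow one pre-specified rule. If missingness differs between arms, the choice of denominator alone can change the apparent treatment difference.

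**Working it through.** **Reading the passages together.** The protocol rule yields responders divided by all randomised subjects in the arm. The SAP ratio yields responders divided by subjects with determinable status. Nothing in SAP 7.5.2.2 restores the protocol rule, and the sensitivity analysis there recodes rescue only. Therefore no stated HiSCR50 analysis scores dropouts as nonresponders.

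**Inputs from the documents.** About 120 subjects randomised 1:1:1, so 40 per arm, with 10% discontinuing before Week 16 (Protocol 9.2, SAP 3.5). The plan's own evaluable number reproduces: 40 × 0.90 = 36 per arm.

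**Inputs assumed.** The documents give no expected HiSCR50 rate. The illustration uses 18 of 40 responders on active and 11 of 40 on placebo, plus various splits of missing subjects. The responder count is held fixed throughout.

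**Formula.** With m the fraction of the arm whose status cannot be determined, SAP rate = protocol rate / (1 − m). At m = 4/40 the factor is 40/36 = 1.11.

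**Protocol rule.** 18/40 − 11/40 = 45.0% − 27.5% = 17.5 points, whatever the missingness. The standard error is √(0.45×0.55/40 + 0.275×0.725/40) = 10.6 points.

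**SAP ratio** (differences taken from unrounded fractions):

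| Undetermined, active/placebo | SAP calculation | SAP difference, points | Protocol difference, points |
|---|---|---|---|
| 4/4 (planned 10%) | 18/36 − 11/36 = 50.0% − 30.6% | 19.4 | 17.5 |
| 2/2 (half of the dropouts confirmed as nonresponders) | 18/38 − 11/38 | 18.4 | 17.5 |
| 6/2 | 18/34 − 11/38 = 52.9% − 28.9% | 24.0 | 17.5 |
| 2/6 | 18/38 − 11/34 = 47.4% − 32.4% | 15.0 | 17.5 |
| 6/2, with 16 responders in each arm | 16/34 − 16/38 | +5.0 | 0 |
| 2/6, with 16 responders in each arm | 16/38 − 16/34 | −5.0 | 0 |

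For the 4/4 row the standard error is √(0.5×0.5/36 + 0.3056×0.6944/36) = 11.3 points. The ratio of difference to standard error goes from 17.5/10.6, about 1.66, to 19.4/11.3, about 1.72.

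**Why 1.11 is an upper figure at 10% dropout.** Subjects who stop treatment may stay in the study (Protocol 7.1), the Week 16 window runs from Day 109 to Day 136 (SAP Table 2), and subjects confirmed as nonresponders stay in the SAP denominator. The 2/2 row, with factor 40/38 = 1.05, shows the effect if half of the dropouts are classified that way.

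**The case against.** The best defence has four parts.

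- Protocol 9.4.1 allows percentages among subjects with assessments available, where appropriate. That is a default for summary presentation; 9.4.6.1 is the specific rule for these endpoints.
- SAP Section 1 says "The SAP should be read in conjunction with the study protocol and the Case Report Forms (CRFs"), and the SAP names ITT as the efficacy set. Neither reconciles a ratio that removes ITT subjects with a rule that keeps them.
- SAP 6.2.3 defines a variable; it is not the analysis section. This stands in part. A reader might infer that the CMH test, exact interval and GEE certainly run on the reduced set. The documents do not say so: SAP 7.5.2.2 is silent, SAP 7.1 mainly describes how missing values are stored, and the GEE text says which visits enter, not how missing responses are treated. What is established is a conflict in the reported proportion that the analysis section does not resolve.
- In the planned equal-dropout case the shift is 1.9 points against a standard error of about 11, so the effect on inference is small. This also stands.

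Two further readings go too far. The SAP rate does not rise in every arm with missing data: the arm needs at least one responder and at least one missing subject who cannot be confirmed as a nonresponder. Nor are the pain endpoints demonstrably the only ones that keep subjects with missing visits: the rescue-use endpoint divides by subjects in the group at the visit, which is ambiguous.

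**Conclusion.** The concern holds: the SAP's HiSCR50 proportion departs from the protocol's nonresponse rule, and Section 8 does not declare it. Through Protocol 9.4.7 the same conflict reaches the exploratory responder endpoints with data-available denominators.

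The SAP rate exceeds the protocol rate by a factor of up to 1.11 at the planned dropout, if no dropout can be classified. A reader might infer a bias in favour of imsidolimab. The documents do not support a direction, since unequal missingness can enlarge or shrink the difference. Only the 10% dropout and the 40 and 36 per arm come from the documents; response rates and missingness splits are assumptions. The figures do not cover post-rescue data. Protocol 9.4.4 sets these to missing, but the SAP repeats that only for the AN-count estimand (7.5.1), and a different treatment of them would change the numerator or remove more subjects from the denominator.

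The point should be fixed but is not critical: testing of secondary endpoints is exploratory (Protocol 9.1, SAP 3.3), and the primary AN-count analysis and its power are unaffected.

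**What to change.** Preferred change, in SAP 6.2.3 and 7.5.2.2:

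- Use all ITT subjects in the arm as the HiSCR50 denominator for the rate, risk difference, exact interval and CMH test.
- Score missing Week 16 HiSCR50 as nonresponse, and keep the observed-case rate as a supplementary table.
- State that the post-rescue rule in Protocol 9.4.4 applies to HiSCR50. Those subjects then count as nonresponders in the main analysis, which makes the rescue-as-failure sensitivity analysis largely redundant; the SAP should say so.
- Apply the same missing-data rule to the exploratory responder endpoints under Protocol 9.4.7.

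Acceptable alternative: keep the observed-case rate as the main analysis, declare and justify it in Section 8 before unblinding, and add the nonresponse analysis as a sensitivity analysis.

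The cost is SAP wording and a derivation flag, with no new data. The downside of the preferred change is that reported response rates are lower, and scoring missing as nonresponse is itself an imputation.

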#### 6.2.4 Exploratory Efficacy Variables

The exploratory efficacy endpoints are as follows:

- **Change from Baseline in AN count at Weeks other than Week 16**
- **Percent change from Baseline in AN count at Weeks other than Week 16**
- **Proportion of subjects achieving AN50 at each visit**

The number of subjects with at least a 50% decrease from baseline in AN count will be calculated at each visit.

$$\frac{\# \text{ of subjects in treatment group with } \frac{(\text{AN count at baseline} - \text{AN count at week } x)}{(\text{AN count at baseline})} \geq 50\%}{\# \text{ of subjects in treatment group with AN count at Week } x}$$

- **Proportion of subjects achieving AN75 at each visit**

For each treatment group, the number of subjects with at least a 75% decrease from baseline in AN count will be calculated at each visit. The proportion of such subjects will be calculated for each treatment group at each visit as:

$$\frac{\# \text{ of subjects with } \frac{(\text{AN count at baseline} - \text{AN count at week } x)}{(\text{AN count at baseline})} \geq 75\%}{\# \text{ of subjects in treatment group with AN count at Week } x}$$

**Proportion of subjects experiencing flare, defined as a  $\geq 25\%$  increase in AN count with an absolute increase in AN count of  $\geq 2$  relative to Baseline at each visit**

The proportion of subjects experiencing flare will be calculated for each treatment group as follows:

$$\frac{\# \text{ of subjects in treatment group experiencing flare at Week } x}{\# \text{ of subjects in treatment group with flare assessed at Week } x}$$

- **Change from baseline in abscess count at each visit**
- **Change from baseline in inflammatory nodule count at each visit**
- **Change from baseline in draining fistula count at each visit**
- **Percent change from baseline in draining fistula count at each visit (for subjects who had non-zero draining fistula counts at baseline)**

- **Change from baseline in calculated composite of abscess, inflammatory nodule, and draining fistula total count at each visit**
- **Percent change from baseline in calculated composite of abscess, inflammatory nodule, and draining fistula total count at each visit**
- **Proportion of subjects achieving HiSCR50 at visits other than Week 16**

The proportion of subjects with at least a 50% decrease from baseline AN count, and no increase in abscesses or draining fistulas in comparison to baseline (HiSCR50) at visits other than Week 16 will be calculated for each treatment group using the formula in **Section 6.2.3**, but with 'Week 16' replaced with 'Week x'.

- **Proportion of subjects achieving Hidradenitis Suppurativa Clinical Response 75 (HiSCR75) at each visit**

The proportion of subjects with at least a 75% decrease from baseline AN count, and no increase in abscesses or draining fistulas in comparison to baseline (HiSCR75) at visits other than Week 16 will be calculated for each treatment group, with HiSCR75 data defined as in **Section 6.2.3**, but with 'Week 16' replaced with 'Week x', and with 50 replaced with 75.

- **Proportion of subjects achieving an HS-PGA of inactive (0) or almost inactive (1) at each visit**

For each treatment group, the number of subjects achieving an HS-PGA of inactive (0) or almost inactive (1) will be calculated at each visit. The proportion of such subjects will be calculated for each treatment group at each visit as:

$$\frac{\text{\# of subjects in treatment group achieving an HS-PGA of inactive (0) or almost inactive (1) at Week } x}{\text{\# of subjects in treatment group with HS-PGA score at Week } x}$$

- **Proportion of subjects with at least 2-point decrease in HS-PGA from baseline at each visit**

This endpoint measures a 2-point decrease in HS-PGA score at a given time point compared to baseline. For each treatment group, the number of subjects with at least 2-point decrease in HS-PGA will be calculated at each visit. The proportion of such subjects will be calculated for each treatment group at each visit as:

$$\frac{\text{\# of subjects in treatment group with at least 2 point decrease in HS-PGA at Week } x}{\text{\# of subjects in treatment group with baseline HS-PGA score } \geq 2 \text{ and HS-PGA score at Week } x}$$

- **Change from Baseline in HS-PGA at each visit**
- **Change from Baseline in calculated composite of abscesses, draining fistulas, and inflammatory and non-inflammatory nodules at each visit**

The change from baseline in calculated composite of abscesses, draining fistulas, and inflammatory and non-inflammatory nodules at Week x will be calculated as the sum of abscesses, draining fistulas, and inflammatory and non-inflammatory nodules at the corresponding visit minus the sum of abscesses, draining fistulas, and inflammatory and non-inflammatory nodules at baseline.

- **Change from baseline in average HS pain NRS at visits other than Week 16**

The intensity of HS average pain will be assessed using numeric rating scale (NRS). The average HS pain NRS will be assessed at the visits specified in the Schedule of Activities in **Section 3.6**. Subjects will be asked to assign a numerical score representing the average intensity over the last 7 days of their HS pain symptoms on a scale from 0 (no symptoms) to 10 (worst imaginable symptoms).

Change from baseline will be calculated as the difference between the HS average pain NRS at Weeks x minus the corresponding baseline value.

- **Percent change from baseline in average HS pain NRS at visits other than Week 16**
- **Change from baseline in worst HS pain NRS at visits other than Week 16**

The intensity of HS worst pain will be assessed using NRS. The worst pain NRS will be assessed at the visits specified in the Schedule of Activities in **Section 3.6**. Subjects will be asked to assign a numerical score representing the HS worst pain intensity over the last 24 hours on a scale from 0 (no symptoms) to 10 (worst imaginable symptoms).

Change from baseline will be calculated as the difference between the HS worst pain NRS at Weeks x minus the corresponding baseline value.

- **Percent change from baseline in worst HS pain NRS at visits other than Week 16**
- **Proportion of subjects with at least 3-point decrease in worst HS Pain NRS from baseline at each visit**

For each treatment group, the number of subjects with at least a 3-point decrease in worst HS Pain NRS will be calculated at each visit. The proportion of such subjects will be calculated for each treatment group at each visit as:

$$\frac{\text{\# of subjects in treatment group with at least 3 point decrease from baseline in worst HS Pain NRS at Week } x}{\text{\# of subjects in treatment group with baseline worst HS Pain NRS score } \geq 3}$$

- **Proportion of subjects with at least 3-point decrease average HS Pain NRS from baseline at each visit**

This endpoint measures a 3-point decrease in average HS Pain NRS at a given time point compared to baseline. For each treatment group, the number of subjects with at least a 3-point decrease in average HS Pain NRS will be calculated at each visit. The proportion of such subjects will be calculated for each treatment group at each visit as:

*# of subjects in treatment group with at least 3 point decrease from baseline in average HS Pain NRS at Week x*

---

*# of subjects in treatment group with baseline average HS Pain NRS score  $\geq 3$*

- **Proportion of subjects requiring rescue medication or treatment at each visit**

For each treatment group, the number of subjects receiving rescue medication or treatment (as defined in **Section 6.1.3**) will be calculated at each visit. The proportion of such subjects will be calculated for each treatment group at each visit as:

---

*# of subjects in treatment group requiring rescue medication or treatment by Week x*

---

*# of subjects in treatment group at Week x*

- **Change from baseline in DLQI scores at each visit**

The Dermatology Life Quality Index (DLQI) questionnaire is a simple 10-question validated questionnaire ([Finlay, 1994](#)). These will be assessed at the visits specified in the Schedule of Activities in **Section 3.6.**. Each item is assigned a value from 0 = not at all to 3 = very much and the score is the sum of the individual items (range from 0 to 30). Additional scoring details are below (Cardiff University School of Medicine, 2021):

- If one question is unanswered, this score is allocated to 0.
- If two or more questions are left unanswered the questionnaire is not scored.
- For question 7:
  - an answer of “Yes” is scored as 3;
  - an answer of “Not Relevant” is scored as 0;
  - an answer of “No” is scored depending on the follow up question: *If “No”, over the last week how much has your skin been a problem at work or studying?* “A Lot” is scored as 2 and “A Little” is scored as 1.

Change from baseline in DLQI at each visit will be calculated as the difference between the DLQI at Week x minus the corresponding baseline value.

- **Change from Baseline in IHS4 score at each visit**

The International Hidradenitis Suppurativa Severity Score System (IHS4) is a composite of the number of nodules, abscesses, and draining tunnels. The IHS4 score is calculated at each visit as:

$$(\# \text{ of nodules at Week x}) + 2 * (\# \text{ of abscesses}) + 4 * (\# \text{ of draining tunnels})$$

The resulting score is labeled as:

- $\leq 3$  is Mild HS;
- 4-10 is Moderate HS;
- $\geq 11$  is Severe HS

The change from baseline in IHS4 score at Week x will be calculated as IHS4 at the corresponding visit minus IHS4 at baseline.

- **Change from Baseline in HiSQoL score at each visit**

The Hidradenitis Suppurativa Quality of Life (HiSQoL) is a patient-reported 17-item questionnaire aimed to measure how much HS has affected the patient's quality of life during the past 7 days. It will be assessed at the visits specified in the Schedule of Activities in **Section 3.6**. Each item is scored as Extremely, Very Much, Moderately, Slightly, and Not at All (4, 3, 2, 1, and 0, respectively). Scores range from 0 to 68, with higher scores representing a more severe disease impact. If a single question item is missing a value from the eCRF, that question item is scored as Not at All (0). If more than one question item is missing at a given visit for a subject, the entire questionnaire is considered missing.

The change from baseline in HiSQoL score at Week x will be calculated as HiSQoL at the corresponding visit minus HiSQoL at baseline.

- **Change from Baseline in HS-PtGA score at each visit**

The Hidradenitis Suppurativa Patient Global Assessment (HS-PtGA) is a single-item questionnaire that asks the subject to assess how HS has influenced their quality of life. Scores are on a 5-point scale from 'Not at all' to 'Extremely', with higher scores indicating more severe impact on quality of life. The change from baseline in HS-PtGA score at Week x will be calculated as HS-PtGA at the corresponding visit minus HS-PtGA at baseline.

- **Proportion of subjects in each response category for the HS-PtGA at each visit**

The Hidradenitis Suppurativa Patient Global Assessment (HS-PtGA) is a single item, self-administered questionnaire, which asks the patient to rate how HS has influenced their quality of life ("Extremely" to "Not at all").

For each treatment group, the number of subjects in each response category for the HS-PtGA will be calculated at each visit specified in the Schedule of Activities in **Section 3.6**. The proportion of such subjects will be calculated for each treatment group at each visit as:

$$\frac{\text{\# of subjects in treatment group in each response category at Week } x}{\text{\# of subjects in treatment group with HS-PtGA score at Week } x}$$

- **Proportion of subjects in each response category for the PGI-C at each visit**

The Patient Global Impression of change (PGI-C) is a single item, self-administered questionnaire, which asks the patient to rate the change in their symptom severity ("Very much better" to "Very much worse").

For each treatment group, the number of subjects in each response category for the PGI-C will be calculated at each visit specified in the Schedule of Activities in **Section 3.6**. The proportion of such subjects will be calculated for each treatment group at each visit as:

$$\frac{\text{\# of subjects in treatment group in each response category at Week } x}{\text{\# of subjects in treatment group with PGI-C data at Week } x}$$

- **Proportion of subjects achieving much improvement according to the PGI-C at each visit**

For each treatment group, the number of subjects achieving improvement (“Much better”, or ‘Very much better”) according to the PGI-C will be calculated at each visit specified in the Schedule of Activities in **Section 3.6**. The proportion of such subjects will be calculated for each treatment group at each visit as:

$$\frac{\text{\# of subjects in treatment group in either improvement response category at Week } x}{\text{\# of subjects in treatment group with PGI-C data at Week } x}$$

- **Proportion of subjects achieving improvement according to the PGI-C at each visit**

For each treatment group, the number of subjects achieving improvement (“A little better”, “Much better”, or ‘Very much better”) according to the PGI-C will be calculated at each visit specified in the Schedule of Activities in **Section 3.6**. The proportion of such subjects will be calculated for each treatment group at each visit as:

$$\frac{\text{\# of subjects in treatment group in any improvement response category at Week } x}{\text{\# of subjects in treatment group with PGI-C data at Week } x}$$

- **Proportion of subjects in each response category for the PGI-B at each visit**

For each treatment group, the number of subjects in each response category for the PGI-B will be calculated at each visit specified in the Schedule of Activities in **Section 3.6**. The proportion of such subjects will be calculated for each treatment group at each visit as:

$$\frac{\text{\# of subjects in treatment group in each response category at Week } x}{\text{\# of subjects in treatment group with PGI-B data at Week } x}$$

- **Change from Baseline in PGI-B at each visit**

- **Proportion of subjects achieving “A little bothered” or “Not at all bothered” for the PGI-B at each visit**

For each treatment group, the number of subjects “A little bothered” or “Not at all bothered” for the PGI-B will be calculated at each visit specified in the Schedule of Activities in **Section 3.6**. The proportion of such subjects will be calculated for each treatment group at each visit as:

$$\frac{\text{\# of subjects in treatment group achieving either “A little bothered” or “Not at all bothered” category at Week } x}{\text{\# of subjects in treatment group with PGI-B data at Week } x}$$

- **Proportion of subjects in each response category for the PGI-S at each visit**

The Patient Global Impression of Severity (PGI-S) is a single-item question, which asks the patient to rate the current severity of the HS (“No Activity” / “Clear Skin”, “Mild”, “Moderate”, and “Severe”).

For each treatment group, the number of subjects in each response category for the PGI-S will be calculated at each visit specified in the Schedule of Activities in **Section 3.6**. The proportion of such subjects will be calculated for each treatment group at each visit as:

$$\frac{\text{\# of subjects in treatment group in each response category at Week } x}{\text{\# of subjects in treatment group with PGI-S score at Week } x}$$

- **Change from Baseline in PGI-S at each visit**
- **Proportion of subjects achieving “Mild” or “No activity” / “Clear skin” for the PGI-S at each visit**

For each treatment group, the number of subjects with either “Mild” or “No activity” / “Clear Skin” response category for the PGI-S will be calculated at each visit specified in the Schedule of Activities in **Section 3.6**. The proportion of such subjects will be calculated for each treatment group at each visit as:

$$\frac{\text{\# of subjects in treatment group with either "Mild" or "No activity" / "Clear Skin" response category at Week } x}{\text{\# of subjects in treatment group with PGI-S score at Week } x}$$

- **Proportion of subjects in each category of Hurley Stage at each visit**

The Hurley system describes 3 clinical stages of HS (Stage I, II, and III). The Hurley stage at a given visit will be determined by the site as the greatest Hurley Stage observed from all involved anatomical regions.

For each treatment group, the number of subjects in each category of Hurley Stage will be calculated at each visit specified in the Schedule of Activities in **Section 3.6**. The proportion of such subjects will be calculated for each treatment group at each visit as:

$$\frac{\text{\# of subjects in treatment group in each response category at Week } x}{\text{\# of subjects in treatment group with Hurley Stage scoring at Week } x}$$

- **Change from baseline in Hurley Stage at Weeks 16, 32, and 40**

The change from baseline in Hurley Stage at Weeks 16, 32, and 40 will be calculated as Hurley Stage at the corresponding visit minus the Hurley Stage at baseline.

- **Proportion of subjects with at least 1-stage decrease in Hurley Stage from baseline at each visit**

This endpoint measures a 1-stage decrease in Hurley Stage at a given time point compared to baseline. For each treatment group, the number of subjects with at least 1-stage decrease in Hurley Stage will be calculated at each visit. The proportion of such subjects will be calculated for each treatment group at each visit as:

$$\frac{\text{\# of subjects in treatment group with at least a 1 stage decrease in Hurley Stage at Week } x}{\text{\# of subjects in treatment group with Hurley Stage scoring at Week } x}$$

